2.3. Estimands

The ICH ⁹ E9 (R1) addendum on estimands ¹⁰ and sensitivity analysis in clinical studies analysis in clinical studies to the guideline on statistical principles for clinical studies became effective on 30 July 2020. Table 1 address the construction of estimands for the primary objectives for Part A

FINAL 10 AUG 2022 Page 29 of 73

[figure not shown]
Protocol CONFIDENTIAL Labcorp Study: 8459270 Sponsor Reference: CRD-740-201

Table 1: Estimands for primary objectives for Part A

Objectives	Estimands/Endpoints
Primary	
To assess the effect of CRD-740 compared to placebo in plasma cGMP at Week 4 in subjects with CHFrEF.	Endpoint: The change from baseline (Day -1) in plasma cGMP at Week 4
	Population : Randomized subjects with CHrEF (EF≤40%) who received at least one dose of CRD-740 or placebo (mITT)
	Treatment: CRD-740 dose or placebo, with or without sacubitril/valsartan, dosed as required.
	Intercurrent Event Strategy:
	Discontinuation of treatment (Treatment policy strategy)
	Subject withdraws consent from further data collection (While on treatment strategy)
	Subject lost to follow-up (While on treatment strategy)
	Population Level Summary : Treatment difference (CRD-740 – placebo) in change from baseline in plasma cGMP values at Week 4.
To assess the safety and tolerability of CRD-740 in subjects with CHFrEF, defined as heart failure with EF ≤40%.	Endpoint: AEs, physical examinations, vital signs, 12-lead electrocardiograms, laboratory safety tests (biochemistry, urinalysis, and hematology)
	Population : Subjects with CHFrEF (EF≤40%) who received at least one dose of CRD-740 or placebo
	Treatment: CRD-740 dose or placebo, with or without sacubitril/valsartan, dosed as required.
	Intercurrent Event Strategy:
	Discontinuation of treatment (Treatment policy strategy)
	Subject withdraws consent from further data collection (While on treatment strategy)
	Subject lost to follow-up (While on treatment strategy)
	Population Level Summary : The proportion of subjects who experience any AE, the proportion of subjects who experience any SAE and the exposure-adjusted incidence rates for AE and SAE in each treatment and dose level group.

[figure not shown]
Abbreviations: AE = adverse event; cGMP = cyclic guanosine monophosphate; CHFrEF = chronic heart failure with reduced ejection fraction; EF = ejection fraction; mITT = modified Intention to Treat; SAE = serious adverse event

FINAL 10 AUG 2022 Page 30 of 73

[figure not shown]

CONFIDENTIAL

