# 3.1.2.4. Handling of Intercurrent Events to Reflect the Clinical Question of Interest

Intercurrent events will be handled through a treatment policy and while on treatment strategy. The following intercurrent events are anticipated during the study:

- Discontinuation of treatment
- Subject withdraws consent from further data collection
- Subject lost to follow

The following table describes how intercurrent events will be collected and handled within the analysis.

Table 3 Handling of Intercurrent Events for the Primary Safety Estimand

Intercurrent event	Data collection and analysis	
Discontinuation of treatment	Patients will be followed, and data collected after the intercurrent event will be used in analysis in line with a treatment policy strategy, i.e., disregarding the occurrence of the intercurrent event	

CONFIDENTIAL

Intercurrent event	Data collection and analysis	
Subject withdraws consent from further data collection	Subject who withdraws consent from further data collection will be analyzed by while on treatment strategy: only safety data collected before the occurrence of the intercurrent event will be included in the analysis.	
Subject lost to follow-up	Subject who is lost to follow-up will be analyzed by while on treatment strategy: only safety data collected before the occurrence of the intercurrent event will be included in the analysis.	

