# 3.1.2.5. Population-level Summary for Comparison between Treatment Conditions

The treatment effect will be quantified by the proportion of subjects who experience any AE, the proportion of subjects who experience any SAE and the exposure-adjusted incidence rates for AE and SAE in each treatment and dose level group.

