### 3.1.2.6. Sensitivity Estimators for the Primary Safety Estimand

No sensitivity analyses will be conducted for primary safety estimand in part A.

CONFIDENTIAL

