#### 5.1.4. Treatment Period

Data collected at Day 1 will be assigned to the Treatment Period unless the time (HH:MM) of data collection and time (HH:MM) of first dose of treatment are both recorded and the data collection time is before the time of first dose of treatment. In this case, the assessment will be assigned to the screening period. If the time (HH:MM) of data collection is not recorded but the protocol and / or eCRF includes an instruction to the effect that all Day 1 assessments are to be performed prior to the first dose of treatment, the data collected at Day 1 will be assigned to the screening period. However, adverse events and medications starting on Day 1, will be assigned to the Treatment Period.

The Treatment Period is defined as the period from the date / time of the first dose of treatment up to and including the date / time of the last dose of treatment.

Treatment period in Part A comprises 3 dosing periods:

Period 1 (dose of ) from date of the first dose of treatment at level till date of the first dose of treatment at level;

Period 2 (dose of ) from date of the first dose of treatment at level till day before Visit 7;

Period 3 (dose of ) from the dose of treatment on Visit 7 till the date of the last dose of treatment.

If subject discontinues during Period 1 or Period 2, the date of the last dose of treatment will be considered as end of the respective period.

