#### 6.7.2. Adverse Events

All AEs recorded on the eCRF will be coded using the MedDRA dictionary [version 24.1 or a later version if updated during the study] and classified as either pre-treatment AEs or treatment—emergent AEs (TEAEs) as follows:

- Pre-treatment AEs are events that start prior to the start of the Treatment Period.
- TEAEs are either events with start date and time after the first study treatment administration or events with start date and time prior to the first study treatment administration whose severity worsening or becoming serious after the start of the Treatment Period.
- The relationship between a TEAE and treatment is assessed as related, or not related. A treatment-related TEAE will be defined as a TEAE considered by the investigator as related to treatment or unknown / missing relationship to treatment.
- The severity of and AE is assessed as Mild / Moderate / Severe according to the investigator. Severe TEAEs are defined as TEAEs assessed as being "Severe" and includes those events where the severity is missing.
- TEAEs leading to discontinuation of study are defined as TEAEs where "Required Withdrawal from study" is indicated as other action taken on AE eCRF form.
- TEAEs leading to discontinuation of study treatment are defined as TEAEs where "Drug Withdrawn" is indicated as action taken with study treatment on AE eCRF form
- TEAEs leading to dose interruption are defined as TEAEs where "Drug Interrupted" is indicated as action taken on AE eCRF form

For Part A, the primary safety analysis will be performed by reporting the exposure-adjusted incidence rates in subject-years for AE and SAE defined as the number of subjects with that particular AE or SAE within a system organ class or preferred term during the relevant period divided by the sum of the at-risk times. For a subject who does not have that particular AE or SAE, the at risk time is the exposure time in each period in years. For a subject who does have

CONFIDENTIAL

that particular AE or SAE, the at risk time is the exposure time until the event occurs in each period in years. The adjusted incidence rates will be presented by system organ class and preferred term for Period 1, and separately for Periods 2 and 3 combined. The Hodges-Lehmann methodology will be used to estimate the within-subject point and interval treatment difference.

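### The primary safety rates stop at last dose, but the safety estimand that lists them handles discontinuation by treatment policy; the exposure formula also drops a day

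*SAP*

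**What the plan says.** **The estimand.** SAP 3.1.2.5 summarises the primary safety estimand by the proportions of subjects with any AE and any SAE, and by the "exposure-adjusted incidence rates for AE and SAE in each treatment and dose level group". For discontinuation of treatment, SAP 3.1.2.4 (Table 3) says that "data collected after the intercurrent event will be used in analysis in line with a treatment policy strategy". Protocol 2.3, Table 1, names the same strategy and the same summaries. On sensitivity analysis, SAP 3.1.2.6 states: "No sensitivity analyses will be conducted for primary safety estimand in part A".

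**The estimator.** SAP 6.7.2 divides the number of subjects with the event in the period concerned by the summed at-risk time. Without the event, "the at risk time is the exposure time in each period in years"; with it, the time is cut at the event. Rates are planned for Period 1 and for Periods 2 and 3 combined. Protocol 8.5 also builds the denominator from exposure time.

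**The periods.** Under SAP 5.1.4, for a subject who stops in Period 1 or 2, "the date of the last dose of treatment will be considered as end of the respective period". Period 3 runs "from the dose of treatment on Visit 7 till the date of the last dose of treatment". Period 1 otherwise runs "till date of the first dose of treatment at level" (dose levels redacted), and Period 2 ends the day before Visit 7.

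**Day counts.** SAP 6.7.1 takes exposure as last dose date minus first dose date, divided by 7. SAP 6.5 counts days on treatment as the same difference plus 1.

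**AE collection.** Protocol Appendix 1 ends AE reporting 28 days after last dose. Protocol 4.3.3 asks subjects who stop drug to attend the remaining visits, and the Appendix 4 schedule marks AE recording through Visit 10 (Day 113).

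**The concern.** The analysis labelled primary for safety should estimate the quantity that the estimand describes. Under treatment policy, an AE that starts after a subject stops drug counts, and so does the time at risk after stopping. As specified, neither does. The gap falls on the subjects for whom the discontinuation strategy was written. If stopping differs between CRD-740 and placebo, the two arms' rates would be truncated to different degrees.

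The day count matters for the same analysis. At-risk time is an exposure time, and the SAP holds two conventions for counting exposure days without saying which one the rates use.

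**Working it through.** **1. Trace a subject who stops on Day 14 and has a new AE on Day 20.** The subject's Period 1 closes on Day 14 and Periods 2 and 3 never open. The event is in neither numerator, and the time after Day 14 is in neither denominator. The same holds for a stop in Period 2 or 3. SAP 6.7.2 specifies no overall exposure-adjusted rate that would pick up the event.

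**2. Where the event still appears.** The SAP 6.7.2 definition of a treatment-emergent AE has no end date. The event therefore counts in the any-AE or any-SAE proportion, in the overall column of the TEAE tables, and in the listings. Only the exposure-adjusted rates miss it.

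**3. Person-time left out.** The documents give no stopping rate, so the fractions here are assumptions. Take an arm of 40 (two thirds of 60), nominal dosing Day 1 to Day 84, and a fraction p stopping on Day 14.
- All 40 followed to Day 84: 40 × 84 / 365.25 = 9.20 subject-years.
- On treatment only, p = 5%: (2 × 14 + 38 × 84) / 365.25 = 8.82. Left out: 0.38, or 0.05 × 70 / 84 = 4.2%.
- p = 10%: (4 × 14 + 36 × 84) / 365.25 = 8.43. Left out: 0.77, or 8.3%.
- p = 20%: (8 × 14 + 32 × 84) / 365.25 = 7.67. Left out: 1.53, or 16.7%.
- p = 0: nothing is left out.

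**4. Direction.** Take p = 10% and 4 subjects with an on-treatment event, and for simplicity do not cut time at the event. The on-treatment rate is 4 / 8.433 = 47.4 per 100 subject-years. Followed to Day 84, one further post-stop event gives 5 / 9.199 = 54.4; no further event gives 4 / 9.199 = 43.5. The rate can move either way.

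**5. End of AE collection.** Last dose on Day 14 gives 14 + 28 = Day 42 under Appendix 1, against Day 113 in the schedule, a 71-day gap. For a completer, 84 + 28 = Day 112, a 1-day gap. Since 56 + 28 = 84, the 28-day limit falls short of Day 84 only for subjects whose last dose is before Day 56.

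**6. Exposure formula.**

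| Dosing days | SAP 6.7.1 as written | With +1 |
|---|---|---|
| 1 | 0 days | 1 day |
| 84 | 83 days (11.86 weeks) | 84 days (12.00 weeks) |
| 15 | 14/7 = 2.00 weeks, in the 2-weeks-or-less category | 2.14 weeks, next category up |
| 29 | 28/7 = 4.00 weeks, in the over-2-to-4 category | 4.14 weeks, next category up |
| 85 | 84/7 = 12.00 weeks, in the over-4-to-12 category | 12.14 weeks, next category up |

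The loss for a completer is 1/84 = 1.2%.

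**7. Period boundaries.** Read as inclusive, Period 1 ends on Day 15, the day on which Period 2 starts. With +1 the periods then sum to 15 + 14 + 56 = 85 days; without it, to 14 + 13 + 55 = 82. With +1 and Period 1 ending on Day 14, they sum to 14 + 14 + 56 = 84.

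**The case against.** The best defence is that rates to last dose are a conventional and useful safety measure. The estimand itself asks for rates by dose level, and off-drug time belongs to no dose level. That stands, and it is why the period rates should be kept and relabelled rather than stretched.

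It is also fair that the practical weight is limited. The proportions in the same estimand can follow treatment policy. AE summaries are descriptive, the sample size was not set by power, and protocol 4.3.3 expects interruption or discontinuation to be rare. This bounds the importance of the mismatch without removing it.

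On the day count, SAP 6.7.2 does not cross-refer to 6.7.1, so the effect of the missing day on the rates is inferred. A nominal 84-day completer stays in the same exposure category either way. The errors for one-day exposures and at the category limits remain.

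On AE collection, two qualifications apply. The active phase in Appendix 1, which ends at the follow-up visit, governs whether an AE is treatment-emergent, not how long AEs are collected. The follow-up paragraph of Appendix 1 also covers events that develop before the final follow-up visit, so the 28-day limit is not a clean rule. What remains is a real ambiguity for subjects who stop early.

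**Conclusion.** The mismatch holds: the exposure-adjusted AE and SAE rates are while-on-treatment quantities listed in an estimand that uses treatment policy for discontinuation. It rests on reading exposure time through the period definitions in SAP 5.1.4, because 6.7.2 does not define the term. It affects early stoppers only. The 4.2 to 16.7% of person-time depends on assumed stopping fractions and an assumed Day 14 stop, and it is a share of time, not an effect on a rate. The day-count error holds independently and is small except for very short exposures and at category limits. Both should be corrected; neither affects alpha or power.

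Four stronger readings are not supported:
- **Post-stop events are lost from safety reporting.** They remain in the proportions, the overall tables and the listings.
- **The rates are biased in a known direction.** No stopping or off-drug event rates are given, and step 4 of the working shows movement either way.
- **The SAP departed from the protocol without declaring it in section 7.** Protocol 8.5 already uses exposure time, so the conflict lies within the protocol.
- **The Hodges-Lehmann estimate contradicts the statement that AEs will not be compared between treatment groups.** The estimate is described as within-subject and the bar is on between-group comparisons. The contrast is undefined, which makes it unclear but not shown to be contradictory.

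**What to change.** 1. Keep the Period 1 and Periods 2 and 3 rates to last dose and label them while-on-treatment.
2. Add one overall exposure-adjusted AE and SAE rate by treatment group. Events and at-risk time should run from first dose to the earliest of first event, end of that subject's AE collection, or a horizon common to stoppers and completers (planned end of treatment, nominally Day 84), regardless of discontinuation. Running it to the end of AE collection for everyone would overshoot: even with no stoppers, 28 of a completer's 112 days (25%) would be off drug.
3. Reconcile protocol Appendix 1 with section 4.3.3 and the Appendix 4 schedule on when AE collection ends for subjects who stop drug but stay in the study. Item 2 depends on this, because a Day 14 stopper's collection could otherwise end at Day 42, well before the common horizon.
4. Add 1 to the SAP 6.7.1 formula, end Period 1 for analysis on the day before the first Period 2 dose so that the periods sum to 84 days, and state that at-risk time uses these definitions.
5. As a minor clarification, say in both protocol 8.5 and SAP 6.7.2 what the within-subject Hodges-Lehmann difference contrasts.

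**Cost.** Items 1 and 4 are SAP wording and programming. Item 2 is one extra table, which mixes on-drug and off-drug time for stoppers and must be read beside the period rates. Item 3 and the protocol half of item 5 concern protocol text, so they need a clarification or amendment with ethics-committee handling.

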Protocol

A Phase 2, Randomized, Double-Blind, Placebo-Controlled Clinical Study to Assess the Effectiveness of CRD-740 in Subjects with Chronic Heart Failure

Protocol Status: Final Protocol Version: 2.1, Date: 10 AUG 2022 Investigational Product: CRD-740

Protocol Reference Number: CRD-740-201 IND Number: 157183 EU CT number: 2022-500087-36-00

Sponsor:

Cardurion Pharmaceuticals, Inc. [name]

Sponsor Signatory:

Executive Director, Clinical Research

Medical Monitor:

[contact]

Information described herein is confidential and may be disclosed only with the express written permission of the sponsor.

FINAL 10 AUG 2022 Page 1 of 73

Protocol CONFIDENTIAL Labcorp Study: 8459270 Sponsor Reference: CRD-740-201

SPONSOR APPROVAL

I have read the following and approve:		
Executive Director, Clinical Research	Date	

FINAL 10 AUG 2022 Page 2 of 73

Protocol CONFIDENTIAL Labcorp Study: 8459270 Sponsor Reference: CRD-740-201

INVESTIGATOR AGREEMENT

I have read the following protocol and agree to conduct the study as described herein		
[Name, Qualification(s)]	Date	_
Principal Investigator		

FINAL 10 AUG 2022 Page 3 of 73

Protocol Labcorp Study: 8459270

SYNOPSIS

Title of study: A Phase 2, Randomized, Double-Blind, Placebo-Controlled Clinical Study to Assess the Effectiveness of CRD-740 in Subjects with Chronic Heart Failure

Indication: Chronic heart failure

Number of study centers: Approximately 100 sites globally

Development phase: 2

Objectives:

Part A

Primary

[figure not shown]
- To assess the safety and tolerability of CRD-740 in subjects with chronic heart failure with reduced ejection fraction (CHFrEF), defined as heart failure (HF) with ejection fraction (EF) ≤40%.
- To assess the effect of CRD-740 compared to placebo in plasma cyclic guanosine monophosphate (cGMP) at Week 4 in subjects with CHFrEF.

Secondary

• To assess the pharmacokinetics (PK) of CRD-740 in subjects with CHFrEF.

FINAL 10 AUG 2022 Page 4 of 73

FINAL 10 AUG 2022 Page 5 of 73

CONFIDENTIAL

Sponsor Reference: CRD-740-201

Methodology/Study design:

This is a Phase 2, two-part, seamless, randomized, double-blind, placebo-controlled, parallel group clinical study. Part A is a dose ranging study in a group of subjects with CHFrEF. Part B is a proof-of-concept study in subjects with either CHFrEF or chronic heart failure with preserved ejection fraction (CHFpEF).

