5.3.1. Dose Modification

No dose modification other than the protocol-specified dose escalation will be permitted.

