#### CONFIDENTIAL Protocol Reference: CRD-740-201

#### 2. Protocol Details

#### 2.1. Overall Study Design

This is a Phase 2, two-part, seamless, randomized, double-blind, placebo-controlled, parallel group clinical study. Part A is a dose ranging study in a group of subjects with Chronic heart failure with reduced ejection fraction (CHFrEF).

[figure not shown]
. An independent data monitoring

committee (DMC) will oversee the study.

By decision of the Sponsor, and unrelated to safety concerns, Part B of the study will not be conducted.

In Part A, eligible subjects with CHFrEF will be randomized to either CRD-740 or placebo in a 2:1 ratio. As shown in **Figure 1** subjects will start Period 1 at a dose of CRD-740 or matching placebo. Subjects will remain in Period 1 for 2 weeks. At Day 15, subjects enter Period 2 and are dosed at CRD-740 or matching placebo. Subjects will continue in Period 2 for 2 weeks. At Day 29, subjects enter Period 3 and continue CRD-740 or matching placebo. Subjects will continue in Period 3 for 8 weeks to complete a total of 12 weeks of CRD-740 or matching placebo. Safety and tolerability will be continuously assessed. A post-study visit will occur at Week 16. Part A will evaluate the effectiveness of CRD-740 in the overall population of subjects with CHFrEF, and possibly in the 2 subgroups defined by sacubitril/valsartan (Entresto) use (yes, no), depending on the number of subjects in each stratum. Randomization will be stratified on Entresto use (yes vs no).

Figure 1 Study schematic of Part A

Abbreviations: D = Day;

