Adverse events will be summarized by treatment group and overall by dose period (Period 1, Period 2, Period 3, pooled Period 2 and Period 3, and overall) for Part A in the SAF.

- An overview of TEAEs including the number and percentage of subjects with at least one of each mentioned TEAE type:
  - o Any TEAE
    - Leading to discontinuation of study
    - Leading to discontinuation of study treatment
    - Leading to death
    - Mild
    - Moderate
    - Severe
  - Any study treatment related TEAE
    - Leading to discontinuation of study
    - Leading to discontinuation of study treatment
    - Leading to death
  - o Any serious TEAE
    - Leading to discontinuation of study
    - Leading to discontinuation of study treatment
    - Leading to death
  - o Any serious study treatment related TEAE
    - Leading to discontinuation of study
    - Leading to discontinuation of study treatment
    - Leading to death
- The number and percentage of subjects reporting each TEAE and the count of number of events will be summarized by SOC and PT for the following types of TEAEs:
  - o All TEAEs
  - o TEAEs Leading to Discontinuation of Study Treatment
  - o TEAEs Leading to Dose interruption
  - o TEAEs Leading to Study Withdrawal
  - TEAEs Leading to Death
  - o TEAEs by Maximum Severity
  - o TEAEs by Relationship to Treatment
  - o TEAEs by Relationship and Maximum Severity
  - Study Treatment related TEAEs
  - Study Treatment Related TEAEs Leading to Discontinuation of Study Treatment

CONFIDENTIAL

- CONFIDENTIAL
  Protocol Reference: CRD-740-201
- o Study Treatment related TEAEs Leading to Death
- Serious TEAEs
- o Serious TEAEs Leading to Discontinuation of Study Treatment
- o Serious TEAEs Leading to Dose Interruption
- Serious TEAEs Leading to Study Withdrawal
- Serious TEAEs Leading to Death
- Study Treatment Related Serious TEAEs
- Study Treatment Related Serious TEAEs Leading to Discontinuation of Study Treatment
- o Study Treatment Related Serious TEAEs Leading to Death
- o Study Treatment Related Serious TEAEs Leading to Study Withdrawal
- The number and percentage of subjects who died will be summarized by the primary reason of death (if available)

In the above summaries, subjects with more than one TEAE within a particular SOC are counted only once for that SOC. Similarly, subjects with more than one TEAE within a particular PT are counted only once for that PT.

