For summaries by maximum severity, subjects with multiple TEAEs within a particular SOC or PT will be counted under the category of their most severe TEAE within that SOC or PT.

Summaries by SOCs and PTs will be sorted by SOCs by their Internationally Agreed Order (MedDRA) and PTs within SOC by descending order of total incidence. Where preferred terms tie PTs will be sorted alphabetically.

No statistical comparisons of AEs between treatment groups will be performed.

All AE data will be listed and Pre-treatment AEs and TEAEs will be presented together. Treatment-emergence status will be flagged in the listing. The listing will present the relative start and stop day of the AE calculated relative to the first dose of treatment and will be presented for those subjects who received at least one dose of treatment. If the AE is "Ongoing" it will be indicated as such in the listing and the relative stop day will not be calculated. Only original dates will be presented in the listing even though the relative day may be based on an imputed date.

In addition, the following listings will be presented:

- Listing of Deaths
- Listing of Serious TEAEs
- Listing of Severe TEAEs
- Listing of AEs Leading to Interruption of Study Treatment
- Listing of AEs Leading to Discontinuation of Study Treatment
- Listing of AEs Leading to Study Withdrawal

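### The primary safety analysis names a within-subject Hodges-Lehmann treatment difference that parallel-group Part A cannot supply; read as a period contrast, it is undefined and confounded with time on study

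*SAP*

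**What the plan says.** SAP 6.7.2 makes exposure-adjusted incidence rates the primary safety analysis for Part A. Each rate is the number of subjects with the event divided by summed time at risk, shown for Period 1 and for Periods 2 and 3 combined. The paragraph ends: "The Hodges-Lehmann methodology will be used to estimate the within-subject point and interval treatment difference". Protocol 8.5 has the same sentence.

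The surrounding text:

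- Design: Part A is a "randomized, double-blind, placebo-controlled, parallel group clinical study" (Protocol synopsis; SAP 2.1 agrees). Each subject is randomized once, 2:1.
- Periods: SAP 2.1 states "Subjects will remain in Period 1 for 2 weeks", then a further 2 weeks in Period 2, then "Subjects will continue in Period 3 for 8 weeks to complete a total of 12 weeks". The order is the same for everyone, and Protocol 5.3.1 adds "No dose modification other than the protocol-specified dose escalation will be permitted".
- Safety estimand (SAP 3.1.2.5): proportions with any AE or SAE, and "exposure-adjusted incidence rates for AE and SAE in each treatment and dose level group".
- Other AE summaries (SAP 6.7.2): "Adverse events will be summarized by treatment group and overall by dose period", the periods being 1, 2, 3, pooled 2 and 3, and overall.
- Comparisons (SAP 6.7.2): "No statistical comparisons of AEs between treatment groups will be performed".

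**The concern.** A within-subject treatment difference needs subjects observed under both treatments, and Part A has none. Whoever programs the sentence must therefore choose a contrast, an arm and a per-subject score that the plan does not give.

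Safety and tolerability is a primary objective, and this statistic would be reported under the label of a treatment difference. For sparse AE terms it can come out as zero with a zero-width interval, which invites reading as precise evidence of no harm. For common terms, unequal period length can pull it away from zero when nothing has changed.

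**Working it through.** **1. Which contrast can be formed?** Total treatment reproduces as 2 + 2 + 8 = 12 weeks, so Periods 2 and 3 together last 10 weeks.

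- *Drug versus placebo within subject.* By design, 0 of about 60 subjects receive both. It cannot be estimated.
- *Drug versus placebo between arms.* This is not within-subject, and it conflicts with the exclusion of between-group AE comparisons in SAP 6.7.2.
- *Period versus period within an arm.* This can be formed, but all subjects follow the same order, so any dose effect is mixed with time on study. In the placebo arm only time changes. The safety estimand names no such summary. The rate in 6.7.2 is a group quantity, so there is no per-subject value to difference.

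**2. How would the period contrast behave?** The inputs below are assumptions except where a source is given:

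- 40 and 20 subjects (60 at 2:1, SAP 2.3);
- a 95% level, matching the intervals in SAP 6.6.1;
- exact signed-rank limits, with zero differences kept;
- difference taken as Periods 2 and 3 minus Period 1.

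*Sparse terms.* The estimate is the median of the n(n+1)/2 pairwise (Walsh) averages: 820 for n = 40 and 210 for n = 20. If k subjects have a positive difference, at most n(n+1)/2 − (n−k)(n−k+1)/2 averages can exceed 0, whatever their size. The upper limit cannot exceed 0 while that count is no larger than the exact critical value, 264 or 52. The lower limit is symmetric.

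- n = 40: k = 7 gives 820 − 561 = 259 ≤ 264; k = 8 gives 820 − 528 = 292 > 264.
- n = 20: k = 2 gives 210 − 171 = 39 ≤ 52; k = 3 gives 210 − 153 = 57 > 52.

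So the interval is exactly [0, 0] when at most 7/40 or 2/20 subjects lie on each side. The estimate is exactly 0 up to 11/40 (385 < 410) or 5/20 (90 < 105) on each side.

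*Common terms, constant hazard, no dose or time effect.* Assume everyone completes both periods and that events are independent across them. Period 1 incidence p implies q = 1 − (1−p)^5 in Periods 2 and 3. On a 0/1 indicator the difference is +1 with probability q(1−p), −1 with probability p(1−q), and otherwise 0. With a, b and z subjects at +1, −1 and 0, the Walsh averages are:

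- +1: a(a+1)/2 times;
- +0.5: az times;
- 0: z(z+1)/2 + ab times;
- −0.5: bz times;
- −1: b(b+1)/2 times.

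Summing trinomial probabilities over all (a, b) gives:

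| p | q | Median estimate | Interval excludes 0, n = 40 | n = 20 |
|---|---|---|---|---|
| 5% | 23% | 0 | about 0% | about 0% |
| 10% | 41% | 0.5 | 8% | 4% |
| 20% | 67% | 0.5 | 64% | 34% |

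The true difference in exposure-adjusted rate is 0 in every row. The per-subject variable also matters. On a rate built as 365.25/days to first event (0 if none), p = 20% gives a simulated median of about 6 per subject-year and exclusion of 0 in about 35% and 19% of arms.

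**3. What changes with other choices?**

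- *Period 1 versus Period 2* (2 versus 2 weeks): at p = 20% the median estimate is 0 and the indicator interval essentially never excludes 0. The shift in the table comes from unequal period length.
- *Zero differences dropped*: if all non-zero indicator differences are +1, every Walsh average is 1 and the estimate is 1, not 0.

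**The case against.** The strongest defence is that Part A is a dose-ranging study. The safety estimand summarizes by dose level as well as treatment, SAP section 7 confirms that doses differ between Day 1 and Day 29, and the sentence directly follows the split into Period 1 and Periods 2 and 3. A within-subject dose-level contrast in the CRD-740 arm is therefore a plausible intention. That stands as a possible reading. It does not rescue the sentence: the contrast would be confounded with time, it has no meaning as a treatment effect in the placebo arm, and the per-subject variable is still missing. The table shells may hold details, but they are not in these documents.

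The magnitudes are also open to challenge, and this stands. They rest on a chosen pairing, incidence, per-subject variable and rule for zeros. The documents give no AE incidences, so the number of terms in either range is unknown.

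A reader might infer that 2 versus 10 weeks is the only within-subject contrast available. The documents do not support that: SAP 6.7.2 also summarizes Period 2 alone, which allows a 2 versus 2 week comparison, still in fixed order. Nor is there an outright contradiction with the exclusion of between-group comparisons. That conflict arises only on a between-arm reading, which the words within-subject argue against.

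**Conclusion.** Wrong as written. The design cannot deliver a within-subject CRD-740 versus placebo difference, and the one reading that can be computed is a period contrast that is undefined, confounded with time and outside the safety estimand. This conclusion needs no numerical assumption. The [0, 0] intervals and the 0%, 8% and 64% figures illustrate the 2 versus 10 week pairing under the assumptions stated and do not predict this trial's results.

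A reader might infer that the primary safety analysis as a whole is unsound. It is not: the group proportions and exposure-adjusted rates do not depend on this step, and no success criterion or stopping rule uses the statistic. The harm is limited to a misleading number under a misleading label. It should be fixed because the fix is cheap.

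**What to change.** Delete the Hodges-Lehmann sentence from SAP 6.7.2, record the departure from Protocol 8.5 in SAP section 7, and rely on the exposure-adjusted rates by arm and period. The cost is one sentence removed and one entry added, with no new output.

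If the sponsor intended a dose-period contrast in the CRD-740 arm, state the arm, the pairing of periods, the per-subject variable, the treatment of zero differences and the confidence level. Label it a descriptive period contrast confounded with time, and do not call it a treatment difference.

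A between-arm Hodges-Lehmann estimate is not a substitute. It would conflict with the exclusion of between-group comparisons. On an event indicator it would also still be exactly 0 at 19/40 versus 0/20, because 21 × 20 = 420 of the 40 × 20 = 800 pairwise differences are 0.
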